3.3.2.9 Concomitant Medications

All concomitant medications taken during the conduct of the study, including those taken for AEs or historical medical conditions, should be recorded in the subject's source documents and eCRF.

3.3.2.9.1 Supplemental Oxygen Use at Rest

The amount of supplemental oxygen (L/min) required at rest will be assessed at all study visits. Any changes in the amount of supplemental oxygen required at rest should be recorded in the subject's source documents and on the concomitant medication eCRF page. Supplemental oxygen should not be introduced after enrollment, unless there is a medical need in the clinical judgement of the Investigator; however, if supplemental oxygen is started after enrollment, the flow should be consistent for all subsequent tests where oxygen is required at rest.

3.3.3 Efficacy

The efficacy of inhaled treprostinil will be evaluated on the following: N-terminal pro-brain natriuretic peptide (NT-proBNP), 6-Minute Walk Distance, Borg dyspnea score, patient global assessment (PGA), and physical activity (actigraphy). Efficacy assessments collected as part of the final visit for Study RIN PH-304 will be used as the Enrollment Visit efficacy assessments for RIN-PH-305 and do not need to be repeated.

3.3.3.1 N-Terminal Pro-brain Natriuretic Peptide

N-terminal pro-brain natriuretic peptide is a biomarker associated with changes in right heart morphology and function (Fijalkowska 2006). Samples for NT-proBNP will be collected at all study visits and must be drawn prior to the 6MWT and study drug administration.

In the event of Sponsor-approved telemedicine visits, NT-proBNP assessments will not be performed.

3.3.3.2 6-Minute Walk Test

The 6MWT is a validated and reliable measure of exercise ability in patients with chronic respiratory diseases (Holland 2014). This study will utilize an unencouraged 6MWT. The 6MWT is to be performed at all study visits. All 6MWTS performed after enrollment must be conducted following at least 10 minutes of seated rest and between 10 to 60 minutes after study drug administration. The 6MWT will be conducted by qualified, trained staff in a designated 6MWT area that meets the requirements described in Appendix [15.1](#).

Pulse oximetry is to be measured continuously prior to, during, and immediately following each 6MWT, as outlined in Section [3.3.2.7](#).

If a study site or subject has implemented protective measures against COVID-19 (eg, use of an alternative 6MWT testing area or use of personal protective equipment [mask, face shield]), all subsequent 6MWTS should be carried out in a generally consistent manner.

In the event of Sponsor-approved telemedicine visits, 6MWT assessments will not be performed, but the subject should continue to wear an actigraph and maintain normal activity.

3.3.3.2.1 Supplemental Oxygen Use During the 6-Minute Walk Test

Subjects receiving supplemental oxygen during any 6MWT should continue to receive the same flow rate for all subsequent 6MWTS. The amount of supplemental oxygen (L/min) required during any 6MWT should be recorded on the concomitant medication eCRF page. Supplemental oxygen should not be introduced after enrollment, unless there is a medical need in the clinical judgement of the Investigator; however, if supplemental oxygen is started after enrollment, the flow should be consistent for all 6MWTS.

3.3.3.3 Borg Dyspnea Score

The Borg dyspnea score is a 0 to 10 scale rating the level of dyspnea experienced during the 6MWT and should be assessed immediately following each 6MWT. Subjects will be asked to rate their shortness of breath on a scale from 0 (no shortness of breath) to 10 (maximal shortness of breath). The Borg dyspnea scale and instructions for rating the level of dyspnea are provided in Appendix [15.2](#).

In the event of Sponsor-approved telemedicine visits, Borg dyspnea assessments will not be performed.

3.3.3.4 Patient Global Assessment

The PGA is used to rate subject fatigue and shortness of breath. Subjects will use their Sponsor-provided smart device from Study RIN-PH-304 for at-home capture of PGA data up to Quarterly Visit 4 (Year 1) or the Discontinuation Visit (whichever occurs first). Subjects will be asked to perform the PGA at the same time as their at-home spirometry assessment. Subjects are encouraged to complete the activity ahead of their scheduled visit. If the PGA is not completed prior to a visit, the subject should complete the PGA during the visit. Assessment of proper use and data capture should be performed by the study site staff at all applicable visits. An example of the PGA can be found in Appendix 15.4.

3.3.3.5 Actigraphy

Daily physical activity, including overall, non-sedentary, and moderate to vigorous physical activity will be measured via a wrist-worn medical grade physical activity monitor (actigraph). Subjects will receive a new Sponsor-provided actigraph at the Enrollment Visit for capture of activity data up to Quarterly Visit 4 (Year 1) or the Discontinuation Visit (whichever occurs first). Subjects will be asked to wear the device continuously with the exception of certain activities of daily living (eg, bathing) or when the device is being charged. Assessment of proper use and data capture should be performed by the study site staff at all scheduled visits.

3.3.4 Exploratory

3.3.4.1

[REDACTED]

[REDACTED]

[REDACTED]

[REDACTED]

[REDACTED]

[REDACTED]

3.3.5 Telephone Contact

Telephone contact will occur weekly during the dose titration period and monthly thereafter for the remainder of the study, as described in Section 7.4. Subjects will also be directed to call the study site or Investigator at any time to discuss study-related issues of concern (AEs, symptoms, tolerability, device issues, etc). Face-to-face interaction may replace telephone contact for the weeks/months where onsite study visits occur and the information can be obtained during the visit. All telephone contact (ie, dosing instructions, reported AEs, and/or medication changes) must be documented on telephone contact sheets and kept in the subject's source documents.

3.4 NUMBER OF SITES

The same study sites that were identified to recruit subjects for Study RIN-PH-304 will be used for RIN-PH-305. Active subjects from Study RIN-PH-304 who meet eligibility criteria will be permitted to enroll in RIN-PH-305.

3.5 NUMBER OF SUBJECTS

The total sample size will be approximately 136 subjects from Study RIN-PH-304 in the **Original Crossover Design** or approximately 314 subjects if the **Contingent Parallel Design** is applied.

3.6 ESTIMATED STUDY DURATION

Subjects will remain in the study from the date their ICF is signed until they withdraw participation, die, are lost to follow-up, or the study ends. It is estimated that the study will last 3 years, but the actual duration may be shorter or longer.

The study is expected to continue until inhaled treprostinil becomes commercially available for PH-COPD or the Sponsor discontinues development for the indication of PH-COPD, whichever occurs first. The Sponsor may discontinue the study for any reason, at any time. The study may also be discontinued if the Investigators and/or Sponsor determine that continuing the study represents a serious medical risk to study subjects.

4 SUBJECT ELIGIBILITY

4.1 INCLUSION CRITERIA

Subjects who meet the following criteria may be included in the study:

1. Voluntarily gives informed consent to participate in the study.
2. Completed Study RIN-PH-304.
3. Females of childbearing potential (defined as less than 1 year postmenopausal and not surgically sterile) must agree to practice abstinence or use 2 highly effective methods of contraception (defined as a method of birth control that results in a less than 1% per year failure rate, such as an approved hormonal contraceptive, barrier method [condom or diaphragm] with a spermicide, or an intrauterine device) for the duration of study treatment and for 48 hours after discontinuing study drug.
4. Males with a partner of childbearing potential must agree to use a barrier method (condom) with a spermicide for the duration of treatment and for at least 48 hours after discontinuing study drug.

4.2 EXCLUSION CRITERIA

Subjects who meet the following criteria are excluded from the study:

1. Pregnant or lactating.
2. Prematurely discontinued Study RIN-PH-304.
3. Intolerant to inhaled prostanoid therapy.
4. Unwilling or unable to use Sponsor-provided devices (actigraph, spirometer, or smart device).
5. Scheduled to receive another investigational drug, device, or therapy during the course of this study.
6. Any other clinically significant illness or abnormal laboratory value that, in the opinion of the Investigator, might adversely affect the interpretation of the study data or subject safety.

4.3 PRESCRIBED THERAPY

There are no restrictions on concomitant medications with the exception of chronic dosing of any other prostanoïd therapy. Subjects who require 29 days or more of such therapy must discontinue from this study.

All concomitant medications taken during the conduct of the study, including those taken for AEs or historical medical conditions, should be recorded in the subject's source documents and eCRF. The amount of supplemental oxygen (L/min) required at rest and/or during any 6MWT should be recorded in the subject's source documents and on the concomitant medication eCRF page.

5 SUBJECT ENROLLMENT

Subjects will retain the same subject number they were assigned in Study RIN-PH-304.

5.1 TREATMENT ASSIGNMENT

This is an open-label study and all subjects will receive treatment with the study drug, inhaled treprostinil. This study is not randomized or blinded.

6 DRUGS AND DOSING (OR TREATMENT PROCEDURES)

6.1 DRUG DOSAGE, ADMINISTRATION, AND SCHEDULE

Treprostinil for inhalation solution (0.6 mg/mL) is delivered via the Tyvaso Inhalation System, which emits a dose of approximately 6 mcg per breath. Subjects will be provided a Tyvaso Inhalation System by the Sponsor.

All subjects who meet eligibility for RIN-PH-305 will transition from Study RIN-PH-304 and initiate inhaled treprostinil at a dose of 3 breaths (18 mcg) QID during waking hours. Study drug doses should be titrated to a target dosing regimen of 15 breaths (90 mcg) QID or the maximum tolerated dose. Dose titrations can occur as rapidly as possible (as directed by the Investigator). Subjects should be instructed to call the study site if they experience any AEs during the dose titration period.

A sample dose escalation schedule is provided in [Table 6-1](#).

Table 6-1 Sample Inhaled Treprostinil Dose Escalation

Study Day ^a	Single Dose	Total Daily Dose
Titrating to maximum dose of 15 breaths QID		
1 to 3	3 breaths QID (18 mcg)	72 mcg
4 to 6	4 breaths QID (24 mcg)	96 mcg
7 to 9	5 breaths QID (30 mcg)	120 mcg
10 to 12	6 breaths QID (36 mcg)	144 mcg
13 to 15	7 breaths QID (42 mcg)	168 mcg
16 to 18	8 breaths QID (48 mcg)	192 mcg
19 to 21	9 breaths QID (54 mcg)	216 mcg
22 to 24	10 breaths QID (60 mcg)	240 mcg
25 to 27	11 breaths QID (66 mcg)	264 mcg
28 to 30	12 breaths QID (72 mcg)	288 mcg
31 (and beyond)	15 breaths QID (90 mcg)	360 mcg

QID, 4 times daily

^a Study day refers to the days on study drug with Day 1 referring to the first dose of study drug.

The above dosing schedule is only a guide. The Investigator may accelerate or decelerate the dosing titration schedule on an individual basis, considering subject safety, tolerability, and functional improvement.

Dose adjustments should be carried out under appropriate medical supervision and in consultation with the appropriate study site staff. Telephone contact between study site staff and subjects should occur prior to each dose adjustment or at least weekly during dose titration (until 15 breaths QID or the maximum tolerated dose is achieved) and monthly thereafter for the remainder of the study, as described in Section 7.4. All telephone contact (ie, dosing instructions, reported AEs, and/or medication changes) must be documented on telephone contact sheets and kept in the subject's source documents.

If subjects are prescribed bronchodilators, study drug should be administered post-bronchodilator use.

6.2 COMPLIANCE

Study drug (used and unused) must be returned to the study site at each visit and will be dispensed/resupplied, as needed. Study site staff must document the number of used and unused ampoules and assess treatment compliance at each visit.

Subjects will be asked throughout the study whether they have been compliant with study drug dosing instructions. If it is determined that a subject is noncompliant, the study site staff must re-educate the subject on proper dosing compliance and its importance. Continued noncompliance may lead to withdrawal of the subject from the study, after consultation between the Investigator and the Sponsor's Medical Monitor or other Sponsor representative.

Subjects will be asked throughout the study whether they have been compliant with actigraphy, spirometry, and smart device use. Assessment of proper use and data capture should be performed by the study site staff at all applicable visits. If it is determined that a subject is noncompliant, the study site staff must re-educate the subject on compliance and its importance.

7 EXPERIMENTAL PROCEDURES

All attempts should be made to have onsite clinic visits. With Sponsor approval, subjects may have telemedicine visits in lieu of onsite visits, as described in Section [7.5](#).

Refer to [Table 3-1](#) for the schedule of times and events and [Table 6-1](#) for a suggested dose titration schedule.

7.1 ENROLLMENT VISIT

Subjects must sign an approved ICF and meet study-specific inclusion and exclusion criteria before any study-related procedures are performed. The following final visit assessments for Study RIN-PH-304 will serve as the Enrollment Visit assessments for RIN-PH-305: demographics, medical history, PE, vital signs, 12-lead ECG, clinical laboratory assessments, NT-proBNP, PFTs, 6MWT, pulse oximetry (oxygenation), and Borg dyspnea score. As such, these assessments and the corresponding eCRF data entry do not need to be repeated.

The following assessments are required prior to study drug administration:

- Urine pregnancy test (females of childbearing potential)
- [REDACTED]

The following assessments are required prior to completion of the Enrollment Visit:

- Re-educate subject on the use of inhaled treprostinil with the Tyvaso Inhalation System, and the actigraphy, spirometry, and smart devices, if needed
- Dispense device accessories, as applicable
- Dispense study drug
- Assess for AEs (from the time of informed consent for RIN-PH-305)
- Assess for changes in concomitant medications (from the time of informed consent for RIN-PH-305)

Subjects will be called mid-week following initiation of study drug and routinely thereafter, as described in Section [7.4](#).

7.2 WEEK 6 VISIT

Subjects are to return to the study site at Week 6 (± 3 days). The following sequence of assessments is recommended:

- Vital signs: weight, RR, HR, and BP (following at least 5 minutes of seated rest; no other measurement or procedure should be performed during the rest period)
- 12-lead ECG (following at least 5 minutes of seated rest; no other measurement or procedure should be performed during the rest period)
- PE
- Serum pregnancy test (females of childbearing potential)
- Blood draws for clinical laboratory assessments and NT-proBNP (NT-proBNP must be drawn prior to the 6MWT and study drug administration)
- PFTs (performed before the 6MWT or after recovery from the 6MWT)
- Study drug administration
- Pulse oximetry (measured continuously prior to, during, and following the 6MWT)
- 6MWT (following at least 10 minutes of seated rest and between 10 to 60 minutes after study drug administration) with documentation of supplemental oxygen requirement, if applicable
- Borg dyspnea score (immediately following the 6MWT)
- Confirm proper use and capture of actigraphy, spirometry, and PGA data
- Assess for AEs
- Assess for changes in concomitant medications
- Dispense study drug/device accessories and assess drug accountability/compliance

In the event of Sponsor-approved telemedicine visits, only the actigraphy, spirometry, PGA, AE, concomitant medication, and drug/device assessments will be performed.

7.3 QUARTERLY VISITS

Subjects are to return to the study site quarterly (± 14 days). The following sequence of assessments is recommended:

- Vital signs: weight, RR, HR, and BP (following at least 5 minutes of seated rest; no other measurement or procedure should be performed during the rest period)
- 12-lead ECG (following at least 5 minutes of seated rest; no other measurement or procedure should be performed during the rest period)
- PE
- Serum pregnancy test (females of childbearing potential)
- Blood draws for clinical laboratory assessments and NT-proBNP (NT-proBNP must be drawn prior to the 6MWT and study drug administration)
- [REDACTED]
- PFTs (performed before the 6MWT or after recovery from the 6MWT)
- Study drug administration
- Pulse oximetry (measured continuously prior to, during, and following the 6MWT)
- 6MWT (following at least 10 minutes of seated rest and between 10 to 60 minutes after study drug administration) with documentation of supplemental oxygen requirement, if applicable
- Borg dyspnea score (immediately following the 6MWT)
- Confirm proper use and capture of actigraphy, spirometry, and PGA data (up to Quarterly Visit 4 [Year 1] or the Discontinuation Visit [whichever occurs first])
- Assess for AEs
- Assess for changes in concomitant medications
- Dispense study drug/device accessories and assess drug accountability/compliance

In the event of Sponsor-approved telemedicine visits, only the actigraphy, spirometry, PGA, AE, concomitant medication, and drug/device assessments will be performed.

7.4 TELEPHONE CONTACTS

Subjects will be called mid-week following initiation of study drug to perform dose titration and discuss study drug tolerability and any study-related issues.

At least weekly telephone contact is required throughout the dose titration period (until 15 breaths QID or the maximum tolerated dose is achieved) to assess study drug tolerability, AEs, concomitant medications, drug/device compliance, and any other study-related issues. Face-to-face interaction may replace telephone contact for the weeks where onsite study visits occur and the information can be obtained during the visit.

At least monthly telephone contact is required after the dose titration period is complete (15 breaths QID or the maximum tolerated dose is achieved) for the remainder of the study to assess study drug tolerability, AEs, concomitant medications, drug/device compliance, and any other study-related issues. Face-to-face interaction may replace telephone contact for the months where onsite study visits occur and the information can be obtained during the visit.

Subjects will also be directed to call the study site or Investigator at any time to discuss any issues of concern (AEs, symptoms, tolerability, device issues, etc). All telephone contact (ie, dosing instructions, reported AEs, and/or medication changes) must be documented on telephone contact sheets and kept in the subject's source documents.

7.5 TELEMEDICINE VISITS

All attempts should be made to have onsite clinic visits. With Sponsor approval, subjects may have telemedicine visits in lieu of onsite visits, if the conduct of an onsite clinic visit poses a safety risk due to the COVID-19 pandemic. The following assessments will be performed during telemedicine visits:

- Confirm proper use and capture of actigraphy, spirometry, and PGA data (up to Quarterly Visit 4 [Year 1] or the Discontinuation Visit [whichever occurs first])
- Assess for AEs
- Assess for changes in concomitant medications
- Assess study drug accountability/compliance
- Confirm receipt of study drug/device accessories
- Confirm the subject is not pregnant (females of childbearing potential)

If the Enrollment Visit is done via telemedicine, study drug and a new actigraph will be shipped from the study site directly to subjects and subjects should begin study drug and actigraphy assessments as soon as they arrive.

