3.2 OVERALL SCHEDULE OF TIMES AND EVENTS

Table 3-1 Overall Schedule of Times and Events

Study Procedures	Treatment Phase			
	Enrollment Visit ^a	Week 6 Visit ^c (±3 days)	Quarterly Visits ^c (±14 days)	Discontinuation Visit ^m
Informed Consent	X			
Subject Eligibility	X			
Demographics and Medical History	X ^a			
Physical Examination ^r	X ^a	X	X	X
Vital Signs ^{e,r}	X ^a	X	X	X
12-Lead ECG ^{e,r}	X ^a	X	X	X
Clinical Laboratory Assessments ^r	X ^a	X	X	X
NT-proBNP ^{n,r}	X ^a	X	X	X
Pregnancy Test ^{d,r}	X ^a	X	X	X
PFTs ^{i,r}	X ^a	X	X	X
Pulse Oximetry ^{h,r}	X ^a	X	X	X
6MWT ^{g,r}	X ^a	X	X	X
Borg Dyspnea Score ^{f,r}	X ^a	X	X	X
Actigraphy ^o	X	X	X	X
At-home Spirometry ^p	X	X	X	X
PGA ^q	X	X	X	X
Dispense Study Drug/Dosing Instructions	X	X	X	
Drug Administration at Study Site ^r	X	X	X	X
Drug/Device Accountability		X	X	X
Adverse Events ^{k,l}	X	X	X	X
Concomitant Medications	X	X	X	X
Telephone Contact ^j		X	X	X
Discontinuation Form				X ^m

6MWT, 6-Minute Walk Test; AE, adverse event; BP, blood pressure; eCRF, electronic Case Report Form; DLCO, diffusion capacity for carbon monoxide; ECG, electrocardiogram; FEV₁, forced expiratory volume in 1 second; FVC, forced vital capacity; HR, heart rate; NT-proBNP, N-terminal pro-brain natriuretic peptide; PE, physical examination; PFT, pulmonary function test; PGA, patient global assessment; PH, pulmonary hypertension; RR, respiratory rate; SpO₂, saturation peripheral capillary oxygenation; TLC, total lung capacity

^a The following assessments - demographics, medical history, PE, vital signs, 12-lead ECG, clinical laboratory assessments, NT-proBNP, PFTs, pulse oximetry (oxygenation), 6MWT, and Borg dyspnea score - will be performed at the final visit for Study RIN-PH-304 and along with the corresponding eCRF data entry, do not need to be repeated at the Enrollment Visit for RIN-PH-305. Assessments to be performed prior to initiation of study drug include a urine pregnancy test for females of childbearing potential and the collection of biomarkers for consented subjects who did not provide blood in Study RIN-PH-304. If the Enrollment Visit is done via telemedicine, study drug and a new actigraph will be shipped from the study site directly to subjects and subjects should begin study drug and actigraphy assessments as soon as they arrive.

^b [REDACTED]

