^c The visit window for the Week 6 Visit is ± 3 days; the visit window for all Quarterly Visits is ± 14 days. Study visits are scheduled based on the date of enrollment in RIN-PH-305 (eg, 6, 13, 26, 39, 52 weeks after the Enrollment Visit). An unscheduled visit may occur at any time and involve any of the procedures deemed appropriate by the Investigator.

^d For females of childbearing potential, a urine pregnancy test should be done at the Enrollment Visit (prior to study drug administration) and serum pregnancy tests at all other visits.

^e Vital signs (weight, RR, HR, and BP) and ECG are to be performed after a 5-minute period of seated rest. No other measurement or procedure should be performed during this 5-minute rest period. When possible, vital signs and ECGs should be collected prior to the 6MWT.

^f See Appendix 15.2. The subject should be asked to rate their maximal breathlessness during the 6MWT immediately following the 6MWT.

^g See Appendix 15.1. All 6MWTS performed after enrollment will be conducted following at least 10 minutes of seated rest and between 10 to 60 minutes after study drug administration. The 6MWT will be conducted by qualified, trained staff in a designated 6MWT area. Subjects receiving supplemental oxygen during any 6MWT should continue to receive the same flow rate at all subsequent 6MWTS. The supplemental oxygen flow rate (L/min) must be recorded at each study visit, as applicable.

^h Pulse oximetry will be performed continuously prior to, during, and immediately following each 6MWT. Pulse oximetry will include the measurement of SpO₂ and HR. The SpO₂ and HR obtained immediately prior to and immediately following completion of the 6MWT will be recorded in the eCRF. In addition, the lowest recorded SpO₂ and associated HR obtained during each 6MWT will be recorded in the eCRF.

ⁱ PFTs will include the evaluation of FEV₁, FVC, TLC, and DLCO. TLC and DLCO will be assessed only when clinically feasible. When possible, PFTs should be performed prior to the 6MWT. If PFTs cannot be performed prior to the 6MWT, they should be performed after recovery from the 6MWT. If PFTs are done both pre- and post-bronchodilator use, only the post-bronchodilator values will be recorded.

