complete the activity ahead of their scheduled visit. If spirometry is not performed prior to a visit, the subject should perform the spirometry assessment during the visit. Assessment of proper use and data capture should be performed by the study site staff at all scheduled visits.

- ^q Subjects will use their Sponsor-provided smart device from Study RIN-PH-304 for at-home capture of PGA data up to Quarterly Visit 4 (Year 1) or the Discontinuation Visit (whichever occurs first). Subjects will be asked to perform the PGA at the same time as their at-home spirometry assessment. Subjects are encouraged to complete the activity ahead of their scheduled visit. If the PGA is not completed prior to a visit, the subject should complete the PGA during the visit. Assessment of proper use and data capture should be performed by the study site staff at all applicable visits.
- ^r Applicable only if an onsite study visit.

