3.3.2.4.2 Pregnancy Testing

Females of childbearing potential will undergo a urine pregnancy test at the Enrollment Visit, prior to study drug administration, and a serum pregnancy test at every visit thereafter. A positive pregnancy test will result in a subject's withdrawal from the study.

In the event of Sponsor-approved telemedicine visits, pregnancy tests will not be performed, but subjects will be asked to verbally confirm they are not pregnant. Verbal confirmation of pregnancy will also result in a subject's withdrawal from the study.

Refer to Section [9.4.2](#) for information related to the reporting and following of pregnancy.

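### At a telemedicine Enrollment Visit, verbal confirmation replaces the pre-dose urine pregnancy test, so the pregnancy exclusion rests on self-report; Section 7.1 and footnote a do not state the exception

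*Combined protocol and SAP*

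**What the plan says.** For a woman of childbearing potential, the ordinary route to the first dose runs through a urine test. Section 7.1 introduces a short list with "The following assessments are required prior to study drug administration", and the urine pregnancy test is on it. Table 3-1 footnote a agrees: "Assessments to be performed prior to initiation of study drug include a urine pregnancy test for females of childbearing potential".

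The telemedicine route is different. Section 3.3.2.4.2 first states the urine-test rule and then, for telemedicine visits that the Sponsor has approved, says that "pregnancy tests will not be performed, but subjects will be asked to verbally confirm they are not pregnant". Footnote r, which is attached to the Pregnancy Test row of Table 3-1, reads "Applicable only if an onsite study visit". Section 7.5 lists confirmation that the subject is not pregnant among the telemedicine tasks. For a telemedicine Enrollment Visit it has the site ship the drug, after which "subjects should begin study drug and actigraphy assessments as soon as they arrive". Footnote a repeats that instruction.

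Exclusion criterion 1 in Section 4.2 is "Pregnant or lactating". Section 7.1 and footnote a also list the RIN-PH-304 final-visit assessments that serve as Enrollment data. A pregnancy test is not among them.

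**The concern.** Enrollment is the visit at which the pregnancy exclusion is applied, and it comes before the first dose in this study. A verbal answer cannot reveal a pregnancy that the subject does not know about, which is the case that a pre-dose test exists to catch. Waiving the test at a follow-up visit delays one check in a series. Waiving it at Enrollment removes the check that decides entry.

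The text also leaves a reader of 7.1 or footnote a alone without the exception. Footnote a sets out the urine-test rule and the ship-and-start instruction together and does not say how one bears on the other. No home kit, local laboratory test or hold on dosing is described.

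At stake are subject protection and clarity about eligibility. The study plans no formal hypothesis tests, and no statistical result depends on this point.

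**Working it through.** The plan gives no figure to reproduce here. The check compares the sections and then works out when the first scheduled test falls.

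**1. Which text governs a telemedicine Enrollment Visit**

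| Place | What it requires before the first dose | Telemedicine exception stated there? |
|---|---|---|
| 7.1 | Urine test | No |
| Footnote a | Urine test | No, although it also gives the ship-and-start instruction |
| 3.3.2.4.2 | Urine test | Yes: verbal confirmation instead |
| Footnote r (Pregnancy Test row) | Row applies to onsite visits only | Yes |
| 7.5 | Verbal confirmation; drug started on arrival | It is the telemedicine section |

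The lead-in to Section 7 sends telemedicine visits to 7.5. Taken together, the specific text prevails: no test is done, a verbal answer is taken, and drug starts when the parcel arrives.

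**2. Whether another step fills the gap before the first dose**

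- Carried-over assessments: no pregnancy test is listed (7.1, footnote a).
- Telephone contact: the first scheduled call follows the start of drug, and pregnancy is not among the listed topics (7.4).
- Contraception (inclusion criterion 3) and the duty to report a suspected pregnancy (9.4.2) lower the risk but do not detect an unrecognised pregnancy.

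**3. Time from enrollment to the first scheduled test**

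Table 3-1 footnote c counts visits from the enrollment date, with windows of ±3 days for Week 6 and ±14 days for Quarterly Visits.

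- Week 6 onsite: 6 × 7 = 42 days; 42 − 3 = 39 and 42 + 3 = 45, so 39 to 45 days.
- Week 6 by telemedicine and Week 13 onsite: 13 × 7 = 91 days; 91 − 14 = 77 and 91 + 14 = 105, so 77 to 105 days.

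These intervals run from enrollment. Time on drug is shorter by the delivery delay, which the documents do not give. They set no limit on consecutive telemedicine visits, though each needs Sponsor approval.

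**4. Number of subjects**

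The planned size is about 136 (crossover design) or 314 (parallel design), from Section 3.5. The share of women of childbearing potential and the share of telemedicine enrollments are not given. I assume 1% to 5% and 5% to 25%.

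- Low: 136 × 0.01 × 0.05 = 0.07
- High: 314 × 0.05 × 0.25 = 3.9

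This counts women who would start drug without a test in this study. The number with an unrecognised pregnancy would be smaller.

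**The case against.** The strongest reply is that this is a considered waiver. Section 3.3.2.4.2 states the rule and its exception in adjacent paragraphs, and 7.5 repeats the verbal check. Telemedicine is allowed only with Sponsor approval and where an onsite visit poses a COVID-19 safety risk, and sites are told to make every attempt to see subjects in person. That stands: the plan made a trade-off under pandemic conditions.

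Three stronger readings are tempting, and the documents do not support them.

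- *A reader might infer that a site starting drug without a test breaches the protocol.* Section 7.1 alone suggests so, but the lead-in to Section 7, 3.3.2.4.2 and footnote r together permit it. What 7.1 and footnote a lack is a statement of the exception.
- *A reader might count footnote d as a further conflict.* It too places a urine test before the first dose, but footnote r limits the same table row to onsite visits, so the table reconciles the two.
- *A reader might infer that such a subject has had no recent test at all.* Enrollment falls on the day of the final RIN-PH-304 visit, and these documents do not say whether that study tests then. Absence from the carry-over list does not settle it.

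It can also be said that a home result is itself reported by the subject and unverified. That is true, but it can reveal a pregnancy of which she is unaware, and a verbal answer cannot.

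**Conclusion.** The point holds as an inexpensive safety improvement with a drafting correction. As written, the plan allows a woman of childbearing potential enrolled by telemedicine to take her first dose in this study on her own word that she is not pregnant. The next scheduled test is about six weeks later, or about thirteen weeks later if Week 6 is also remote. The wording is clear enough that most sites would act this way. The remaining inconsistency is confined to 7.1 and footnote a.

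The intervals follow directly from the visit schedule. That few subjects are affected rests on assumed shares, and the range is wide because the documents supply neither share. A pregnancy test at the final RIN-PH-304 visit would reduce the gap, but these documents do not show one.

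**What to change.** In 7.5 and footnote a, add: *If the Enrollment Visit is held by telemedicine, a urine pregnancy test is sent with the study drug, and a female of childbearing potential must report a negative result to the site before her first dose.* In the telemedicine paragraph of 3.3.2.4.2, and in footnote r as it applies to the Pregnancy Test row, add: *except the Enrollment urine test.* Section 7.1 can then stand as it is.

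If the Sponsor prefers verbal confirmation alone, the alternative is to state that exception, with its reason, in 7.1 and footnote a.

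The Enrollment test is a urine test, unlike the later serum tests, so it can go in the parcel that the site already ships. The cost is one kit and one reported result per subject concerned, with the first dose held until that result is in. The result is read at home and unverified. No visit is added. The change is a short amendment, which under Section 13.1 needs regulatory and IRB/IEC approval before it takes effect.
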